Appendix 5: Prescription of GRASPA

GRASPA-AML 2012-01, Prescription form, version 2.0, dated 11 Oct 2015_FR

ETUDE GRASPA-AML2012-01 PRESCRIPTION DE GRASPA[®] (eryaspase, dispersion pour perfusion)

IDENTIFICATION DU CENTRE
IP nom :
Adresse du centre :
No centre :
N° FAX :

FAXER A

ERYTECH PHARMA

N° [contact]

IDENTIFICATION DU	PATIENT							
NOM				Monog	ramme	N° Patient		
PRENOM				 Nom	- Prénom	N° Centre N° Patient		
Né(e) le	Jour	_ mois	année	Sexe		1 🗆 F		
Poids du patient			Kg					
PRESCRIPTION				•				
l poche de sur la base du dossier j Préciser si caractéristique t	e GRASPA [®] pré transfusion particulière (d	compatible onnel du par	tient ci-joint	Dose 1 0	0 UI/Kg	5		
			gatii).					
Date et heure prévue d'administration	 Jour	_ mois	année		_ _ H	mn		
ELEMENTS DU DOSSII	ER PRE TR	ANSFUSIC	ONNEL DU PA	TIENT				
 Photocopie de la carte ATTENTION LE PROD de 72h, A faxer dans les 2 En cas de difficulté, appe Date : 	 □ Photocopie de la carte de groupe sanguin valide ATTENTION LE PRODUIT SERA EXPEDIE UNIQUEMENT APRES RECEPTION DES RAI de moins de 72h, A faxer dans les 2 jours précédent l'administration. En cas de difficulté, appeler immédiatement le Pharmacien ERYTECH Pharma au [name] Date : Nom du prescripteur : Signature : 							
LIVRAISON PHARMA	CIE							
ADRESSE : [
Tél.:]			Fax.: [· 		
CONTACT POUR LA RE Nom(s), fonction(s):	CEPTION D	DE GRASPA	[®] (MENTION	OBLIGAT	OIRE POU	JR L'EXPEDITION)		
	Cadr	e réservé El	RYTECH pour d	confirmation	l			
Dose 1 0 0 UI/Kg	Dose to	tale : _	UI	Date Signa	ture :			
RAI ATTENDUES POUR	LE							
PG-CLI-001-F7			Indice A	·	Revis	se le 25/03/2013		

This document, exclusive property of ERYTECH PHARMA, must not under any circumstances whatsoever, be transmitted to a third party, photocopied, or reproduced without prior authorization

GRASPA-AML 2012-01, Prescription form, version 2.0, dated 11 Oct 2015_EN GRASPA-AML2012-01 STUDY PRESCRIPTION OF GRASPA® (eryaspase, dispersion for infusion)

SITE IDENTIFICATIO	N	TO E	BE FAXED AT:		
PI name:		EDV	ИТЕСН РНАРМА		
Site address:		EKYI	ECH PHARMA		
Site No.:	•••••	FAX	No: [name]	
FAX No:					
PATIENT IDENTIFICA	ΓΙΟΝ				
LAST NAME			Patient Initials	Patient No	
FIRST NAME			- Last Name First name [Site No Pat No	
Date of Birth	day month year		Gender □ M	□ F	
Weight	Kg				
PRESCRIPTION					
l compatible bag of pretran	GRASPA [®] , according patient sfusionnal status	ţ	Dose:  1 0 0  IU/Kg		
Precise specific conditions	required if any (i.e. CMV negation	ive):			
Administration scheduled on the	 day month year		at	h min	
PATIENT PRETRANSF	USIONNAL STATUS TO BE	ATTA	CHED :		
Number of pages (includin	g this prescription sheet) : p	ages			
Completed "BLOOD GRO	OUP FORM"				
WARNING: GRASPA®	WILL BE SENT ONLY AFTE 72 H (3 DAYS) PRIOR G	CR REO GRASP	CEPTION OF IAST R A [®] INFUSION	ESULTS LESS THAN	
In case of any difficul	ty, please contact ERYTECH	Pharm	na Pharmacist Tel No -	[name]	
Date :	Investigator Name :		Signature :		
DELIVERY ADDRESS					
ADDRESS :					
Tel.:	Fa	x. / Ma	il.:]	
CONTACT (MANDATO	RY FOR SHIPMENT) Name(s), funct	tion(s):	1	
]	
	Reserved as per confirm	ation b	by ERYTECH		
Dose: 1 0 0 IU/Kg	Total Dose : _ _ _	IU	Date & Signature :		
DATE IAST expected :					

This document, exclusive property of ERYTECH PHARMA, must not under any circumstances whatsoever, be transmitted to a third party, photocopied, or reproduced without prior authorization

GRASPA-AML 2012-01

Protocol Version 07, dated 05 Oct 2015

- CONFIDENTIAL -

Appendix 6: Transport and injection forms

DOCUMENT DE TRANSPORT ET D'INJECTION DE GRASPA®

1- ERYTECH PHARMA - ENVOI DE GRASPA [®] ORIGINAL							
Date de Prescription Mise en	par le Dr/Pr.:	_ année année	Etique Identité	ette Poche avec patient complète			
expedition	Par (transporteur) :						
	2- F	HARMACIE -	RECEPTION DE GRASP	A®			
Date de récep	tion	année	Horaire h	_ min			
Contrôle qua	lité de la poche Conform	e Non Confo	rme Documents et mat	ériel joints Présent Absent			
Identification	de patient		Carte de contrôle				
Intégrité Transfuseur double voie (Tubulures de rincage)							
Température Emballage pour retour de poche							
Personne ayan	Personne ayant réceptionné le produit (Nom, fonction) :						
Date et heure de sortie du froid : à h min							
par (Nom, fon	ction) :		Fin de mise à fr	oid, produit à injecter dans les 6 heures .			
3- UNITE DE SOIN - ADMINISTRATION DE GRASPA®							
Vérification de la prescription :							
Vérification patient/étiquette produit : Oui Non							
Contrôle ultime au lit (compatible) :							
Date d'administration : $ </td							
Produit administré : Dui Totalement Partiellement Non							
Rinçage des tubulures : Oui Non							
Cause de non conformite, non injection ou non rinçage							
Administration effectuée par : Date : Signature jour mois année							
RAPPEL : Retour de la poche à ERYTECH Pharma selon modalités							
DOCUMENT COMPLETE A FAXER SANS DELAI AU [name] (Pharmacien ERYTECH Pharma)							
Référence	e: SOP-LOGI-002-F4		Indice : B	Date d'application : 24/11/2014			

 Référence : SOP-LOGI-002-F4
 Indice : B
 Date d'application : 24/11/2014

 Ce document est la propriété de ERYTECH PHARMA. Il ne peut être ni reproduit, ni communiqué à un tiers sans autorisation d'une personne mandatée spécialement à cet effet par ladite société

ORIGINAL

Etape 1 : RECEPTION DE LA POCHE

- Réception de la poche sous responsabilité pharmaceutique par le Pharmacien de la PUI.
- Effectuer les contrôles à réception selon la rubrique « *Réception de GRASPA*[®] » au verso de ce document.

Etape 2 : ADMINISTRATION

- Appliquer les règles de vérification ultime (identité, examen du produit, contrôle ultime de compatibilité au lit du patient entre le GRASPA[®] et le sang du malade)
- ▲ Dans le cas où le patient a reçu une transfusion non programmée depuis la prescription de GRASPA[®], réaliser avant l'injection une épreuve de compatibilité auprès de votre laboratoire d'immunohématologie (segment à disposition sur le produit).
- \triangle En cas d'anomalie, le produit ne devra pas être transfusé.
- Transfuser la totalité de la poche
- Rincer les tubulures avec du sérum physiologique (20 à 40 ml de NaCl 0,9%)

Etape 3 : TRACABILITE

- Compléter la section « *Administration de GRASPA*[®] » au verso de ce document.
- Faxer le Document de transport et d'injection de GRASPA[®] complété (sections remplies) sans délais au [name]
- Conserver le Document de transport et d'injection de GRASPA[®] dans le dossier médical du patient

Etape 4 : RETOUR DE LA POCHE (à ERYTECH Pharma)

- Après administration, placer la poche vide dans le sachet prévu à cet effet (ne pas joindre les tubulures)
- Se reporter à la procédure de retour pour effectuer l'enlèvement par le transporteur

GRASPA[®] SHIPMENT AND ADMINISTRATION FORM

1- ERYTECH PHARMA - SHIPMENT OF GRASPA [®] ORIGINAL							
Prescription date	escription date By Dr/Prof.:						
Shipping date	day month By (carrier) :	_ year					
	2- RECEP	TION OF GRASP	$A^{ extsf{\$}}$ To be filled in by the	e Recipient			
Reception Da	Reception Date Time min						
Quality Cont	rol of the bag Conform	Non Conform	Related supply		Present Absent		
Patient Identif	fication						
Integrity Infusion double line (allowing rinsing) Temperature Packaging for bag return							
Recipient Name: Signature:							
Removing from +2+8°C - Date/Time : at h min							
by (Name) : _			y e	To be administered wi	thin 6 hours		
3- ADMINISTRATION OF GRASPA®							
Consistency w	with prescription	Yes	🗌 No				
Check patient identification vs label :							
Ultimate cross match blood test :							
Administration Date : Start : h h min End : h min day month year Year <t< td=""></t<>							
Product administered :							
Infusion line rinsing :							
Reason for non-conformity, administration failure, rinsing failure, or any relevant comment							
Administration performed by: Date : _ _ _ Signature day month year							
PLEASE FAX THIS DOCUMENT COMPLETED TO [name] (ERYTECH Pharmacist)							
D / 4/							
Référence Ce document e	e : SOP-LOGI-002-F4 st la propriété de ERYTECH PHARMA. Il ne p	ut être ni reproduit, ni commur	lice : B iqué à un tiers sans autorisation d'une i	Date d'application	on: 24/11/2014		

Step 1 : RECEPTION OF GRASPA[®]

- Under medical responsibility.
- Check items as indicated in section *«Reception of GRASPA[®]»* in the *«GRASPA[®] shipment and administration form ».*

Step 2 : ADMINISTRATION

• Prior to the administration, an ultimate compatibility cross match test should be performed between patient blood and GRASPA[®] received using segment tube.

▲ If the patient received a blood transfusion in between GRASPA[®] prescription and scheduled date of administration of GRASPA[®], a new compatibility test should be performed in your local laboratory.

 $\boldsymbol{\Delta}$ In case of discrepancy the product must not be administered.

- The entire content of the bag must be infused.
- Rinse the perfusion line with NaCl 0,9% (around 20 to 40 mL).

Step 3 : DOCUMENTATION

- Complete the *«Administration of GRASPA[®]»* section of the document *«GRASPA[®] shipment and administration form».*
- Fax completed «GRASPA[®] shipment and administration form» form shortly after administration to [name].
- Keep the document «GRASPA[®] shipment and administration form» completed together with patient medical file.

Step 4 : RETURN OF THE BAG (To ERYTECH Pharma)

- After administration, put the bag of GRASPA[®] into the supplied packaging for return (please do not insert perfusion lines).
- Follow the instructions to have the package picked.

Schritt 1: ANNAHME DES BEUTELS

- Unterliegt ärztlicher Verantwortung.
- Kreuzen Sie die entsprechenden Punkte im Abschnitt «Reception of GRASPA[®]» des Dokuments «GRASPA[®] shipment and administration form» an.

Schritt 2: VERABREICHUNG

- Vor der Infusion ist mittels Segmentröhrchen und Blutgruppenkarte eine endgültige Kreuzprobe zur Überprüfung der Kompatibilität zwischen Patientenblut und zu verabreichendem GRASPA[®] durchzuführen.
- ▲ Hat der Patient zwischen der Verordnung und der eigentlichen Infusion von GRASPA[®] eine Bluttransfusion erhalten, muss im Labor Ihrer Einrichtung ein erneuter Kompatibilitätstest durchgeführt werden. Im Falle von abweichenden Ergebnissen darf das Produkt nicht infundiert werden.
 - Es muss der gesamte Beutelinhalt infundiert werden.
 - Spülen Sie die Perfusionsleitung mit 0,9% iger Kochsalzlösung (etwa 20 bis 40 ml).

Schritt 3: DOKUMENTATION

- Füllen Sie Abschnitt *«Administration of GRASPA[®]»* im Dokument *«GRASPA[®] shipment and infusion form»* aus.
- Faxen Sie das Dokument «GRASPA[®] shipment and administration form» mit den ausgefüllten Abschnitten zeitnah nach der Infusion an folgende Nummer: [name].
- Bewahren Sie das ausgefüllte Dokument «GRASPA[®] shipment and administration form» zusammen mit der Krankenakte des Patienten auf.

Schritt 4: RÜCKGABE DES BEUTELS (an ERYTECH Pharma)

- Stecken Sie nach Verabreichung von GRASPA[®] den Beutel in die mitgelieferte Verpackung f
 ür R
 ücksendungen (legen Sie bitte keine Perfusionsleitungen bei).
- Folgen Sie den Anweisungen, um das Päckchen abholen zu lassen.

Etapa 1: RECEPCIÓN DE LA BOLSA

- Recepción de la bolsa bajo responsabilidad médica
- Al recibir el producto, realice los controles de la sección «Reception of GRASPA[®]» en el documento Envío de GRASPA[®] y Administración «GRASPA[®] shipment and administration form»

Etapa 2: ADMINISTRACIÓN

- Antes de la administración, una prueba de compatibilidad definitiva debe ser realizada, entre la sangre del paciente y GRASPA[®] recibido, usando un tubo de segmento y la tarjeta sanguínea
- ▲ En el caso de que el paciente haya recibido una transfusión no programada desde la prescripción de GRASPA[®], hasta la fecha programada de la administración de GRASPA, un nuevo test de compatibilidad debe ser realizado en su laboratorio local.
- \triangle El producto no debería ser administrado en caso de discrepancias.
- Infunda toda la bolsa
- Purgar la línea de perfusión con suero fisiológico (de 20 a 40 ml de NaCl al 0,9%)

Etapa 3: DOCUMENTACIÓN

- Rellene la sección *«Administration of GRASPA[®]»* del documento Envío de GRASPA[®] y Administración *«GRASPA[®]* shipment and administration form».
- Envíe cuanto antes, después de la administración por fax el Documento «GRASPA[®] shipment and administration form» cumplimentado al [name]
- Conserve este Documento en la historia clínica del paciente

Etapa 4: DEVOLUCIÓN DE LA BOLSA (a ERYTECH Pharma)

- Tras la administración, coloque la bolsa vacía en el sobre previsto para ello (no incluya las líneas de perfusión)
- Consulte el procedimiento de devolución para realizar la recogida por el transportista

Fase 1: RICEVIMENTO DELLA SACCA

- Ricevimento della sacca sotto responsabilità medica
- Eseguire i controlli alla consegna descritti dalla voce *«Reception of GRASPA[®]»* del Documento *«GRASPA[®] shipment and administration form»*

Fase 2:SOMMINISTRAZIONE

- Attenersi alle regole di verifica finale (identità, esame del prodotto, controllo finale di compatibilità subito prima della somministrazione al paziente fra GRASPA[®] e il sangue del malato)
- ▲ Nel caso in cui il paziente abbia ricevuto una trasfusione non programmata dalla prescrizione di GRASPA[®], eseguire prima dell'iniezione un test di compatibilità presso il laboratorio di immunoematologia della vostra struttura (segmento disponibile sul prodotto).
- \triangle In caso di anomalie, il prodotto non deve essere trasfuso.
- Somministrare per trasfusione tutto il contenuto della sacca
- Sciacquare i tubi con soluzione fisiologica (20-40 ml di NaCl al 0,9%)

Fase 3: TRACCIABILITÀ

- Compilare la sezione *«Administration of GRASPA[®]»* a tergo di questo documento.
- Inviare immediatamente per fax il Documento «GRASPA[®] shipment and administration form» completato (sezioni compilate) al [name]
- Conservare il Documento di trasporto e di iniezione di GRASPA[®] nella cartella clinica del paziente

Fase 4: RESTITUZIONE DELLA SACCA (a ERYTECH Pharma)

- Dopo la somministrazione, mettere la sacca vuota nel sacchetto previsto per tale scopo (non aggiungere i tubi)
- Richiamarsi alla procedura di restituzione per provvedere al ritiro da parte del trasportatore

GRASPA[®] VALMISTEEN VASTAANOTTO JA ANTO

1. vaihe: PUSSIN VASTAANOTTO

- Pussin vastaanotto vastuullisesti lääketieteellisten käytäntöjen mukaan
- Suorita vastaanottotarkistukset « *Reception of GRASPA*[®] » ja injektioasiakirjan kohdan «GRASPA[®] shipment and administration form» mukaisesti
 - 2. vaihe: ANTO
- Tarkista valmiste äärimmäisen tarkkojen tarkistussääntöjen mukaan (tunnistetiedot, valmisteen tutkiminen, GRASPA[®]-valmisteen ja sairaan henkilön veren yhteensopivuuden tarkistaminen viime kädessä potilaan vierellä).
- ▲ Jos potilas on saanut GRASPA[®]-valmisteen määräämisen jälkeen verensiirron, jota ei ole etukäteen merkitty ohjelmaan, teetä ennen injektiota yhteensopivuustutkimus immuno-hematologisessa laboratoriossa (osio valmisteen päällä).
- Δ Jos havaitaan poikkeamia, valmistetta ei saa antaa potilaaseen.
- Anna pussin koko sisältö.
- Huuhtele letkut fysiologisella keittosuolaliuoksella (20 40 ml 0,9-prosenttista NaCl-liuosta).

3. vaihe: JÄLJITETTÄVYYS

- Täytä kappale « *Administration of GRASPA*[®]» joka on tämän asiakirjan toisella puolella.
- Lähetä «GRASPA[®] shipment and administration form» ja injektioasiakirja täydennettynä (osiot täytettyinä) viipymättä faksilla numeroon [name]
- Säilytä GRASPA[®]-valmisteen kuljetus- ja injektioasiakirja potilaan asiakirjojen joukossa

4. vaihe: **PUSSIN PALAUTTAMINEN (ERYTECH Pharmalle)**

- Kun valmiste on annettu, aseta tyhjä pussi sille varattuun kuljetuspussiin (älä laita letkuja mukaan).
- Pyydä kuljetusyritystä noutamaan lähetys palautusprosessia koskevien ohjeiden mukaisesti.

GRASPA-AML 2012-01

- CONFIDENTIAL -

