8.4 Study treatment administration

All patients enrolled, randomized in Arm A or B, will receive successive 28-day courses of subcutaneous low-dose cytarabine 40 mg daily (or 20 mg twice daily) for 10 days per course (from day 1-D1 to day 10-D10), each course occurring every 28 days +/- 3 days, for a duration up to 24 months. SPC for Cytarabine Hospira and Pfizer are attached in Appendix 1 as example. Please refer to country-specific approved Cytarabine SPC for country-specific information.

Following the implementation of Amendment 4, patients randomized in arm B treatment will receive subcutaneous low-dose cytarabine, as described above, and GRASPA 100 IU/kg, given as an intravenous infusion at **Day 11** of each 28-day course.

Required documents such as **Investigator's prescription of GRASPA and Patient's pretransfusional status** (refer to section 9.6) should be sent at ERYTECH Pharma 2 days before the schedule day of GRASPA administration, i.e. Day 9.

In the event the patient cannot receive GRASPA treatment at the planned date (i.e. manufacturing failure) or if GRASPA treatment received on site is not suitable for administration (e.g. transport or cold chain impairment, rupture of bag...), investigator and ERYTECH Pharma will discuss the best treatment approach for the patient:

- Restart manufacture for a new bag of GRASPA (delay GRASPA administration with max one week), if acceptable for the patient.
- Switch the patient to appropriate alternative treatment, at investigator's decision.
 - If the switch occurred before the first GRASPA administration, then the patient will be replaced, as defined in section 7.6.
 - If the switch occurred after at least one administration of GRASPA, treatment for next blocks afterwards will be at investigator's decision (GRASPA will not be resumed if delayed more than 2 weeks; refer to section 8.5.4 "Dosage modifications of GRASPA" and 8.11 "end of study treatment").

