8.10 Study visits assessments and procedures

• Inclusion Visit (within max 4 weeks before treatment initiation):

During the inclusion visit, the following procedures/assessments will be performed:

- Patient information about potential study participation and obtaining the signed informed consent before any study related procedures;
- Patient demographics: date of birth, gender;
- ECOG performance status
- AML characteristics and assessment (see section 8.6): qualitative and quantitative parameters, primary diagnostic date, baseline values for bone marrow blast count, cytogenetic analysis, FAB and WHO classifications, including extramedullary AML assessment
- Medical history (relevant for the study condition) and concomitant medications
- General physical examination by systems and organs, including routine ECG, weight and height measurements
- Biological assessment (see section 8.7.1 for detailed items): date of sample taken; assessed and signed anonymized lab reports must be sent to sponsor/representatives Inclusion and exclusion criteria validation
- Patient registration in IWRS system
- Patient randomization if all criteria are met.
- Subsequent visits : from visit 1 onwards:
 - Disease evaluation (AML) (see section 8.6)
 - Clinical assessment: vital signs (height, weight, pulse, blood pressure systolic and diastolic), performance status (ECOG score), physical examination findings
 - Study treatment administration (low-dose cytarabine +/- GRASPA): details on date and time of administration are required
 - Patient quality of life: survey EORTC QLQ-C30, transfusion needs, hospitalizations from any cause (except scheduled protocol visit)
 - Biological assessment at D1, D5, D9, D13, D18, D23, D27 (see section 8.7.1 and table 4 for detailed items) instructions to be provided to patient in case of lab testing outside the site hospital; assessed and signed anonymized lab reports must be sent to sponsor/representatives as soon as possible after sampling
 - PK-PD and immunogenicity testing (see section 8.7.2, Table 4 and 5 and Appendix 3 for detailed instructions) only patients on arm B (under GRASPA treatment)
 - IAST (Irregular Antibodies Screening Test) at D9 only patients on arm B (under GRASPA treatment)
 - Review and assessment of any adverse event (refer to section 11 for details)
 - Record of any change in concomitant medications
 - Distribution of patient diary and instructions provided to patients for completion for each visit

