9.5 Precaution for use

Anaphylaxis or serious allergic reactions: Patients should be constantly monitored during the infusion and at least one hour after the end of the infusion. Discontinue GRASPA with serious allergic reactions.

Coagulation disorders: Blood count and clotting profile should be monitored before and during treatment with GRASPA. In cases of anti-thrombin III deficiency, administration of anti-thrombin III concentrate is preferable to transfusion of fresh frozen plasma (FFP) as it could counteract the GRASPA activity.

Hepatotoxicity: Hepatic enzymes should be monitored before and regularly during treatment with GRASPA. Treatment with GRASPA should be discontinued in the event of bilirubin levels >3 times upper limit of normal or transaminase levels >10 times upper limit of normal.

Pancreatitis: Serum lipase and amylase should be monitored regularly. Treatment with GRASPA should be discontinued in patients with Grade 4 pancreatitis.

Glucose intolerance: L-asparaginase may cause hyperglycemia and patients with diabetes may have aggravation of their condition. Blood glucose levels should be monitored regularly.

Cardiac or renal impairment: Patients should be monitored for evidence of volume overload. The speed of infusion of GRASPA should be slowed as needed.

If a patient receives a blood transfusion between the prescription of GRASPA and its administration, new compatibility tests must be performed.

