9.6 Prescription

GRASPA is manufactured for one patient at a time according to investigator's prescription.

To initiate the manufacture, ERYTECH Pharma should be provided with the documents listed hereafter:

- **Prescription Sheet** indicating patient identifiers as well as his weight, the investigator recipient of the product, the place and the time of delivery. A template of the prescription sheet is available in Appendix 5: Prescription of GRASPA
- Validated Erythrocyte phenotype and **ABO blood group card** with 2 determinations
- an IAST (Irregular Antibody Screening Test) performed at the local immunohematology laboratory, less than 72h prior to GRASPA transfusion

In the event the IAST is positive, or in case of previous or history of positivity, a compatibility test is mandatory. Therefore, a 5 mL sample of patient's blood should be sent to EFS Lyon (Service Immuno-hématologie, Hôpital Edouard Herriot pavillon I, [name]. N° [contact] n° [contact])

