9.7 Supply, transportation, receipt and storage conditions

GRASPA bag is shipped to Investigator's site in a qualified box allowing keeping medicinal product at controlled temperature $+2^{\circ}$ C to $+8^{\circ}$ C. The temperature evolution during shipment is continuously monitored by a recording sensor inside the pack.

Details regarding GRASPA reception should be documented by the recipient on the document "GRASPA Shipment and administration Form" (Appendix 6):

- Patient information consistency
- The integrity of the bag of GRASPA (absence of visual leak),
- The temperature indicator attached to the bag must show no sign that the product underwent out of range temperature. Otherwise, the investigator must contact ERYTECH Pharma for further instructions.
- The expiry date is compatible with the date and time of administration
- Presence of control card and Infusion double line (allowing the rinsing)

Presence of a Packaging for bag return

GRASPA should be managed and administered by the physician-investigator's department as soon as possible upon receipt and within the expiry time stated on the label.

The current shelf life of the product is 72 h from end of manufacture when stored between +2 °C to +8 °C (See the mention on the label).

GRASPA can be kept at room temperature up to a maximum of 6 hours before the injection (including the injection time). The product remains stable as showed in the stability studies. Do not freeze.

Instruction for receipt and administration of GRASPA are detailed in Appendix 6. Any issue happen, please contact ERYTECH Pharma for immediate appropriate recommendation.

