9.8 Administration

Before administration of GRASPA, the following controls must be performed and should be recorded on the document "GRASPA Shipment and administration Form" (Appendix 6):

- The general appearance of the bag. The statements on the label are adapted according to the clinical trial.
- The product for color; dark red color should be observed. If it provides evidence that the product underwent excessive or low temperatures during shipment, the investigator must contact ERYTECH Pharma for further instructions. He/she will then determine whether to urgently request a new preparation.
- Presence of the document "GRASPA Shipment and Administration Form".

Consistency of information on "GRASPA Shipment and Administration Form" and the patient: name, forename, date of birth.

• An ultimate cross match blood test to check compatibility. Expiry date is compatible with date and time of administration.

If there is any doubt, the product must not be administered.

A compatibility test (cross-match) test between the patient's blood and GRASPA (removable segment tubes) should be performed in your local laboratory and GRASPA must not be administered in case of discrepancy.

GRASPA should not be administered beyond the maximum shelf life stated on the label.

GRASPA should not be transferred to another container before injection. Since no data regarding incompatibility are available, GRASPA should not be mixed or administered simultaneously with any other product, solution or medicinal product.

The administration should take place within the expiry time stated on the label of GRASPA.

GRASPA is administered by intravenous route using line devices provided with the product, under medical responsibility. If a pump is used, only devices specifically approved for blood transfusion should be used.

The rate of transfusion depends on the patient's clinical conditions. The mean duration for administration is about 45 minutes, longer in case cardiac impairment and must be adapted regarding the volume of the bag and patient's clinical conditions.

The entire content of the bag must be administered. The patient must remain awake and should be constantly monitored during the injection for occurrence of any adverse reactions and should be kept under observation for at least one hour post administration. In case of occurrence of a major symptom (e.g. malaise), GRASPA injection should be stopped immediately and the principal investigator must be informed.

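### Four of the six Appendix 6 instruction sheets require a repeat compatibility test only after an unscheduled transfusion, although section 9.5 requires it after any; three also omit the section 9.8 segment-tube cross-match

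*Protocol*

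**What the plan says.** Two sections of the protocol body set the rule.

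- Section 9.5: "If a patient receives a blood transfusion between the prescription of GRASPA and its administration, new compatibility tests must be performed". It makes no distinction between planned and unplanned transfusions and does not say where the test is done.
- Section 9.8 lists, among the controls before administration, "An ultimate cross match blood test to check compatibility". It then asks separately for a cross-match of each bag against the patient, in these terms: "GRASPA (removable segment tubes) should be performed in your local laboratory and GRASPA must not be administered in case of discrepancy". Neither control depends on a transfusion having been given.

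Section 9.7 sends sites to the appendix: "Instruction for receipt and administration of GRASPA are detailed in Appendix 6". Appendix 6 holds six instruction sheets (French, English, German, Spanish, Italian, Finnish) and two record forms (French and English). Step 2 of the French sheet opens its laboratory-test line with: "Dans le cas où le patient a reçu une transfusion non programmée depuis la prescription de GRASPA".

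On timing, section 8.4 has the prescription and pre-transfusion documents sent "2 days before the schedule day of GRASPA administration, i.e. Day 9", and section 8.10 schedules the "IAST (Irregular Antibodies Screening Test) at D9 only patients on arm B". Under section 9.6 that screen must be dated "less than 72h prior to GRASPA transfusion".

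**The concern.** The translations are meant to carry one set of instructions, yet they differ on a transfusion-safety step, and four of them are narrower than the protocol body. The site has the sheet in hand when the bag arrives, so the narrower wording is likely to be followed.

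Transfusion is expected in this population; the need for red-cell or platelet transfusion is a secondary endpoint in section 4.3.2. A planned transfusion between Day 9 and Day 11 is therefore a realistic event. At a site using the French, Italian or Finnish sheet, it would not lead to the new test that section 9.5 requires, and the routine step would not supply the laboratory cross-match either. The stake is patient safety and consistent handling across countries. No endpoint, error rate or analysis is involved.

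**Working it through.** No formula applies to the main point. The check sets Step 2 of each sheet against sections 9.5 and 9.8.

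| Sheet | New laboratory test is triggered by | Routine check for each bag |
|---|---|---|
| English | any transfusion since prescription | cross-match using the segment tube |
| German | any transfusion since prescription | cross-match using the segment tube and blood-group card |
| Spanish | unscheduled transfusion only (*no programada*) | compatibility test using the segment tube and blood card |
| French | unscheduled transfusion only (*non programmée*) | bedside compatibility check; no segment tube, no laboratory |
| Italian | unscheduled transfusion only (*non programmata*) | final check just before administration; no segment tube, no laboratory |
| Finnish | only a transfusion not entered in the programme beforehand | bedside compatibility check; no segment tube, no laboratory |

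Counts from the table:

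- Trigger matches section 9.5: English and German, 2 of 6.
- Trigger narrower than section 9.5: French, Spanish, Italian and Finnish, 6 − 2 = 4 of 6.
- Narrower trigger, but a segment-tube test kept for every bag: Spanish, 1 of 6.
- Narrower trigger and no segment-tube cross-match in the routine check: French, Italian and Finnish, 4 − 1 = 3 of 6. In all three, the bag segment is mentioned only inside the line on unscheduled transfusions.

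The second question is whether the age limit on the antibody screen would force a repeat test anyway.

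- Screen at Day 9 (section 8.10), infusion at Day 11 (section 8.4): 11 − 9 = 2 days, and 2 × 24 = 48 h.
- Age limit 72 h (section 9.6): 72 − 48 = 24 h to spare.
- Whatever the clock times, Days 9, 10 and 11 span at most 3 × 24 = 72 h from the first minute to the last. A screen taken on Day 9 therefore stays in date on Day 11.

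A patient screened on Day 9, transfused as planned on Day 10 and infused on Day 11 still has an in-date screen that predates the transfusion. The age limit does not by itself trigger a new test.

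The documents give no transfusion frequency in this window, no planned share and no number of sites per language, so the number of infusions affected cannot be estimated.

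**The case against.** The best case against the point has four parts.

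1. *The protocol body already covers the gap.* Sections 9.5 and 9.8 apply whatever the sheet says, and 9.8 forbids administration in case of doubt. This is true, and it means the plan as a whole does not drop the test. But section 9.7 directs sites to Appendix 6, and a sheet with a narrower condition invites a site to stop there.

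2. *Italian and Finnish sites complete the English record form, which has a line for a final cross-match.* This is correct and partly offsets the omission in those two sheets. The line names neither the segment tube nor the laboratory, and it corresponds to the final check that those sheets already contain. Section 9.8 states the segment-tube laboratory cross-match separately. The French form has only a bedside-check line.

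3. *The Spanish sheet tests every bag with the segment tube before infusion, so much of what section 9.5 seeks is already done.* This carries weight. The Spanish sheet is at fault only on the trigger, and the practical consequence there is smaller than for the other three.

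4. *Other safeguards exist.* Red cells are selected for blood type and antibody-screen compatibility (section 9.1), the prescription form holds shipment until a screen under 72 h old is received, and a positive screen, current or past, makes a compatibility test mandatory (section 9.6). All of these can be satisfied before a Day 10 transfusion, so none is the new test that section 9.5 asks for.

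It might also be argued that a planned transfusion is already allowed for at prescription. Section 9.5 makes no such exception, and section 9.6 does not ask about planned transfusions.

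**Conclusion.** The point holds: the sheets are wrong as written and should be corrected. Four of six restrict the repeat laboratory test to an unscheduled transfusion, contrary to section 9.5. Three of those four also leave the section 9.8 segment-tube laboratory cross-match out of the routine check. The full gap, no laboratory compatibility test after a planned transfusion, arises under the French, Italian and Finnish sheets. The Spanish sheet has the trigger error alone.

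This rests on reading section 9.5 as covering every transfusion between prescription and infusion, which is what its wording says, and on sites working from the sheet in their own language, as section 9.7 implies. All six sheets keep some final compatibility check, and the documents do not show that any test was missed or any patient harmed. The English, German and Spanish sheets do not say where the routine segment-tube test is done, and the English record line repeats a control listed in section 9.8; neither is counted as a defect.

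**What to change.** - Delete the qualifier limiting the trigger: *non programmée* (French), *no programada* (Spanish), *non programmata* (Italian), and the Finnish relative clause saying that the transfusion was not entered in the programme beforehand. Any transfusion after prescription then triggers the new test, as in the English and German sheets.
- In Step 2 of the French, Italian and Finnish sheets, add the section 9.8 cross-match on the segment tubes in the local laboratory, and keep the existing final check.
- On the French record form, keep the bedside line and add a separate line for the laboratory cross-match.
- Leave the English record line unchanged, and add no bedside check to the English, German or Spanish sheets.
- Reissue the forms with a short note to sites explaining the change.

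The cost is a form revision, retranslation and reissue. Nothing is asked of sites beyond what sections 9.5 and 9.8 already state, and sample size and analysis are unaffected.
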